CRITERIA FOR EVALUATION: Safety: The following safety outcome measurements will be assessed: 
• Incidence of AEs and SAEs• Vital signs (heart rate, blood pressure, respiratory rate, and temperature)• Physical examination (including neurological assessment)• Hip clinical assessment• Laboratory test results (urinalysis, chemistry, hematology)• Electrocardiogram (ECG)		

NAME OF COMPANY BioMarin Pharmaceutical Inc. [name]	SUMMARY TABLE Referring to Part of the Dossier: Volume: Page:	FOR NATIONAL AUTHORITY USE ONLY:
NAME OF FINISHED PRODUCT: BMN 111		
NAME OF ACTIVE INGREDIENT: Modified rhCNP	Reference:	

 • Echocardiogram • Anti-BMN 111 immunogenicity assessments • Cortisol levels • Prolactin levels 		

Efficacy: The following efficacy outcome measurements will be assessed:
 
 • Change from baseline in AGV • Change from baseline in length/height Z-score 
Pharmacokinetics: Whenever possible, the following PK parameters will be estimated by non-compartmental analysis:
 
 • Area under the plasma concentration-time curve from time 0 to infinity (AUC_{0-∞}) • Area under the plasma concentration-time curve from 0 to the time of last measurable concentration (AUC_{0-t}) • Maximum plasma concentration (C_{max}) • Time to reach C_{max} (T_{max}) • Elimination half-life (t_{1/2}) • Apparent clearance of drug (CL/F) • Apparent volume of distribution based upon the terminal phase (V_z/F) 
Drug accumulation after repeat-dose administration will also be evaluated. PK parameters at Week 13, 26, 39 and 52 will be compared to Day 1. The impact of immunogenicity (if present) on PK will also be evaluated.
 
Bone metabolism and BMN 111 pharmacodynamic biomarkers:
 
 • Changes in bone and collagen metabolism and BMN 111 activity will be assessed. 
Clinical outcome assessments:
 
 • Bayley-III • WeeFIM • CBCL • ITQOL 
Exploratory: The following exploratory measurements will be assessed:
 
 • Upper:lower body segment ratio • Imaging assessments (X-rays of the spine and lower extremities) • MRI to define skull and brain morphology (including dimensions of foramen magnum, ventricular and brain parenchymal dimensions) • Sleep study • Clinical photography (optional) 		

NAME OF COMPANY BioMarin Pharmaceutical Inc. [name]	SUMMARY TABLE Referring to Part of the Dossier: Volume: Page:	FOR NATIONAL AUTHORITY USE ONLY:
NAME OF FINISHED PRODUCT: BMN 111		
NAME OF ACTIVE INGREDIENT: Modified rhCNP	Reference:	

STATISTICAL METHODS:

Sample Size Determination: Approximately 70 subjects age 0 to < 60 months at study entry will participate in this study. No formal sample size calculations were performed. The number of subjects is considered appropriate to evaluate the safety and efficacy of BMN 111 in the target population.

Safety Analysis: All subjects who receive at least one dose of study treatment or who are randomized to the placebo-control group in this study will be included in the safety analysis. The safety analysis will be descriptive.

All AEs will be coded using the most current version of Medical Dictionary for Regulatory Activities (MedDRA) to assign system organ class and preferred term classification to event and disease, based on the original terms entered on the eCRF. The incidence of AEs will be summarized by system organ class, preferred term, relationship to study treatment as assessed by the investigator, seriousness, and severity. All AEs, including SAEs and AEs that lead to permanent discontinuation from the study and from the study treatment, will be listed.

All other safety measures including laboratory tests, vital signs, ECG, echocardiogram, hip clinical assessment, and concomitant medication data will also be summarized descriptively. Data summaries will be presented by treatment group (when applicable) for each cohort and overall. All safety results will be listed.

Efficacy Analysis:

All randomized subjects who receive at least one dose of study treatment or placebo in the study will be included in the efficacy analysis.

Efficacy variables, including AGV (based on length/height) and length/height Z-score according to normal reference standards (not ACH), along with their change from baseline will be summarized by treatment group and cohort. Comparisons between treatment groups by cohort on these variables will be carried out where appropriate. Statistical comparisons will be considered descriptive. 95% CIs will be provided along with p values for treatment group comparisons.

Sentinel subjects will be summarized apart for both efficacy and safety.

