The PK parameters for BMN 111 were obtained from Part 1 of the study and from the first dose on Day 1 of the multiple dose study in Part 2. The results demonstrate that BMN 111 was rapidly absorbed in human, reaching a mean time to peak concentration (T_{max}) between 15-26 minutes. After reaching maximal plasma concentrations, BMN 111 levels rapidly declined, with a $t_{1/2}$ of 40-55 minutes. Mean plasma concentration-time profiles indicate that exposure increased with dose from 2.5 to 15 $\mu\text{g}/\text{kg}$. The corresponding increases in plasma C_{max} and area under the curve (AUC) exposure parameters were greater than dose proportional. The increase in C_{max} with dose was linear over the dose range evaluated. In Part 2, with multiple dosing at 5 $\mu\text{g}/\text{kg}$ for 10 days, the plasma concentration-time curves obtained on each of the three sampling days were nearly superimposable. Comparison of PK exposure parameters for AUC and C_{max} indicate that C_{max} is unchanged and AUC is

increased slightly by +33% over Day 1. Overall the results indicate that changes in BMN 111 exposure are minimal with repeat dosing out to 10 days.

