^j Growth measures may be collected in triplicate approximately the same time each day (\pm 2 hr around the time when the first measurement assessment was taken at Screening). Measurements may include but are not limited to length, standing height (if able to stand unsupported), crown-to-rump length, head circumference, upper and lower arm and leg, and arm span. Measurements not taken in the midsagittal plane should be taken on the right side of the body if possible and should always be taken on the same side of the body throughout the study.

^k Clinical labs (hematology, chemistry, and urinalysis) are all pre-dose draws samples and can be drawn anytime during the visit if there is no drug administration.

^l Plasma samples will be collected pre-dose and at 5 (\pm 2 min), 15 (\pm 2 min), 30 (\pm 5 min), 45 (\pm 5 min), 60 (\pm 5 min), 90 (\pm 5 min), and 120 (\pm 5 min) minutes post-dose. On Day 1, additional PK samples will be collected at 180 (\pm 5 min) and 240 (\pm 5 min) minutes. Samples with volume remaining after pharmacokinetic assessment will be used for cGMP pharmacodynamics assessment. NOTE: In the event of interruption of study drug administration for a sentinel patient on Day 1 when PK samples are scheduled, the collection of PK samples should be delayed until the subsequent day and only performed after successful administration of study drug has been completed in a single injection.

^m Antibodies: Total anti-BMN 111 (TAb), TAb cross-reacting with endogenous natriuretic peptides, and neutralizing antibody (NAb) samples (serum) will be drawn pre-dose at each time point listed on the SOE. TAb cross-reacting with endogenous natriuretic peptides and NAb testing will be performed only on baseline and TAb positive samples from subjects weighing \geq 7.0 kg and waived for subjects $<$ 7.0 kg. Drug-specific IgE will be drawn pre-dose on Day 1 for subjects weighing \geq 7.0 kg and waived for subjects $<$ 7.0 kg to stay within the limits of permitted blood volume collections in infants. Total immunoglobulin E (IgE) and drug-specific IgE will be drawn in the event of Grade 3 hypersensitivity adverse event) or at Investigator or Sponsor discretion. If such an event occurs, the drug-specific IgE sample should be drawn at least 8 hours after the event start time or before the next dose. A sample for total IgE and serum tryptase should be drawn within an hour of the start of the event when possible or during an unscheduled safety visit.

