The criteria for dose adjustment are based on obtaining equivalent exposure characterized to be safe and effective with the 15- μ g/kg dose in Study 111-202 in each of the age cohorts evaluated in this study. BMN 111 dose may be adjusted if the mean observed AUC_{0-120} from

sentinel subjects is less than the 25th percentile for AUC₀₋₁₂₀ in Cohort 3 (15 µg/kg) of Study 111-202 or greater than the 75th percentile in Cohort 3 of Study 111-202. If these criteria are met, an allometric scaling coefficient, α , for BMN 111 clearance by subject body weight will be determined using a population PK modelling approach and available data from this study and Studies 111-202 and 111-101. The recommended adjusted dose will be determined using the following expression:

$$Dose_{ch} = Dose_{ref} \left(\frac{WT_{ch}}{WT_{ref}} \right)^\alpha$$

where WT_{ref} and $Dose_{ref}$ are the typical (i.e., median) subject body weight and total dose, respectively, at the 15 µg/kg dose level in Cohort 3 of Study 111-202, and WT_{ch} is the anticipated median weight in the age cohort being studied. As such, the recommended adjusted dose will target the median AUC₀₋₁₂₀ observed at the 15 µg/kg dose level of Study 111-202. The recommended adjusted dose, $Dose_{ch}$, will be normalized by WT_{ch} , to provide the recommended adjusted weight-based dose. The following rules will be used for dose adjustment:

- A maximum of a 2-fold increase in dose/kg will be permitted between dose adjustments regardless of exposure.
- The total dose will not exceed the highest total dose administered in Study 111-202.

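### Day 1 PK is sampled to 240 minutes and later visits only to 120, so comparing AUC0-t with Day 1 is biased downward wherever Day 1 levels are measurable beyond 120 minutes

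*Protocol*

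**What the plan says.** The pharmacokinetics part of the amended synopsis (Criteria for Evaluation) lists seven non-compartmental parameters, each to be estimated where possible: AUC0-inf, AUC0-t, Cmax, Tmax, half-life, CL/F and Vz/F. AUC0-t is the "Area under the plasma concentration-time curve from 0 to the time of last measurable concentration". The synopsis then says "Drug accumulation after repeat-dose administration will also be evaluated" and "PK parameters at Week 13, 26, 39 and 52 will be compared to Day 1". It adds that the impact of immunogenicity on PK will be evaluated, which is also part of a secondary objective in Section 8.

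The sampling times are in footnote l of Table 9.1.1 (amended). At every PK visit plasma is drawn pre-dose and at 5, 15, 30, 45, 60, 90 and 120 minutes. "On Day 1, additional PK samples will be collected at 180" and 240 minutes; no later visit has these two samples.

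An AUC over a fixed 0-120 minute window is used in Section 9.1.1, where it triggers dose adjustment and "the recommended adjusted dose will target the median" AUC0-120 of Study 111-202. AUC0-120 is not in the PK parameter list. Section 9.11.5 is visible only in the protocol text before the amendment; it has the same seven parameters and the same sampling times.

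**The concern.** AUC0-t has no fixed upper limit. It can cover up to four hours on Day 1 but at most two hours at Weeks 13 to 52. If the curve is the same at both visits and still measurable after 120 minutes on Day 1, the later AUC0-t is smaller only because sampling stopped earlier. The error runs in one direction and occurs with an unchanged dose.

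Two questions the study sets itself are exposed. A real rise in exposure over time could be partly or wholly cancelled. A false fall at Week 13 and later could also look like antibody-related loss of exposure, since antibodies are sampled on Day 1 and at Weeks 3, 13, 26 and 52. A change in AUC over repeat dosing has been seen before: in Study 111-101 (Section 7.2.1) AUC "increased slightly by +33% over Day 1" while Cmax was unchanged.

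**Working it through.** The protocol gives no figure for this comparison, so there is none to reproduce. The check asks what AUC0-t ratio the sampling times produce when nothing has changed.

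**Inputs from the protocol**
- Sampling times: Table 9.1.1, footnote l.
- Adult half-life 40-55 min and Tmax 15-26 min: Study 111-101, Section 7.2.1.
- Once-daily dosing: Section 9.4.1.

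**Assumptions**
- One compartment with first-order absorption.
- The assay's quantification limit and the half-life under 5 years are not given. The last measurable Day 1 sample is therefore varied over 120, 180 and 240 min, and the half-life over 20-55 min.

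**Formulas**
- ke = ln 2 / half-life; ka solves Tmax = ln(ka/ke)/(ka - ke).
- C(t) is proportional to [ka/(ka - ke)] x [exp(-ke t) - exp(-ka t)].
- AUC by linear trapezoid on the protocol's nominal times. An unbiased ratio is 1.00.

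**The two ends of the adult range** (AUC in arbitrary units)

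| Half-life / Tmax (min) | ke; ka (per min) | AUC to 120 | AUC to 180 | AUC to 240 | 120/180 | 120/240 |
|---|---|---|---|---|---|---|
| 40 / 15 | 0.0173; 0.169 | 49.18 | 54.83 | 56.83 | 0.897 | 0.865 |
| 55 / 26 | 0.0126; 0.0868 | 58.36 | 69.73 | 75.06 | 0.837 | 0.778 |

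**False fall in AUC0-t with no true change**
- Adult kinetics, Day 1 measurable to 240 min: ratio 0.78-0.87, a fall of 13-22%.
- Adult kinetics, Day 1 measurable to 180 min: ratio 0.84-0.90, a fall of 10-16%.
- Day 1 unmeasurable after 120 min: ratio 1.00.
- Half-life 20-30 min, measurable to 240 min: ratio 0.89-0.97, a fall of 3-11%.

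**Is measurability beyond 120 min plausible?** Under adult kinetics the predicted level is 18-36% of Cmax at 120 min, 6-17% at 180 min and 2-8% at 240 min. A quantification limit at 5% of Cmax leaves bias in every adult case examined. At 10% bias remains in some cases, and at 20% in none.

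**What could be cancelled.** With Day 1 measurable to 240 min, the true rise that reads as no change is 1/0.865 - 1 = 16% to 1/0.778 - 1 = 29%. A 33% rise of the whole curve would read as 1.33 x 0.778 = 1.03 to 1.33 x 0.865 = 1.15. If the 33% came instead from slower elimination (ke divided by 1.33, ka fixed), the AUC0-t ratio would be 0.89-1.03, the AUC0-120 ratio 1.15-1.19, and Cmax would rise only 4-8%.

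**Other parameters**
- Cmax is unaffected, because Tmax lies well inside 120 min.
- AUC0-inf, with the terminal slope fitted on 60-120 min at later visits and 120-240 min on Day 1, gives a ratio of about 0.99. At later visits about 14-26% of the area is extrapolated.
- Carry-over: 1440/55 = 26 to 1440/40 = 36 half-lives per dosing interval, so 1/(1 - exp(-1440 ke)) is 1.0000000.

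**The case against.** **The comparison does not rest on AUC0-t.** A reader might infer that it does. In fact the synopsis compares PK parameters as a group and singles none out. With flat Cmax, half-life and CL/F beside a lower AUC0-t, a careful analyst would suspect the window. This stands, and it limits the harm to readings that rely on AUC0-t. The protection is partial: AUC0-inf and CL/F at later visits depend on the extrapolated 14-26%, and Cmax did not move in Study 111-101 when AUC did.

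**The bias is conditional.** It needs measurable Day 1 levels beyond 120 minutes, and the documents give neither the assay limit nor the half-life in this age group. This stands in full; the adult-based figures are a range under assumptions.

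**Accumulation cannot be hidden in the usual sense.** This also stands. Carry-over is nil at these half-lives, and the synopsis reports none apparent in adults. Only a time-dependent change in exposure could be obscured.

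**The 33% is not a target.** It came from adults given 5 µg/kg for 10 days, and the protocol calls such changes minimal. It serves here only as a scale for the bias.

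**The SAP could settle the window.** It could, and AUC0-120 is recoverable from the planned samples. But the protocol itself fixes the schedule, the parameter and the comparison, and as stated they do not fit together.

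**Conclusion.** The point holds in conditional form. Wherever Day 1 levels are measurable beyond 120 minutes, the later/Day 1 AUC0-t ratio is biased downward. The size is about 10-22% under the adult half-life and Tmax, about 3-11% if the half-life were 20-30 minutes, and zero if Day 1 levels are unmeasurable after 120 minutes. These figures assume one-compartment kinetics, and the upper ends assume measurability to 240 minutes.

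The documents do not support saying that the whole PK comparison is biased or that carry-over accumulation would be masked. Dose adjustment already uses AUC0-120 and is untouched. This is a modest defect in a descriptive analysis, worth correcting because the correction is nearly free.

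**What to change.** Add AUC0-120 to the PK parameter list in the synopsis and the matching PK variables section (9.11.5). State that the partial-AUC comparison of Weeks 13, 26, 39 and 52 with Day 1, and the antibody-PK comparison, use the common 0-120 minute window instead of AUC0-t. Report AUC0-t beyond 120 minutes for Day 1 only. Keep Cmax, AUC0-inf, half-life and CL/F as supportive comparisons, and report the percentage of AUC0-inf extrapolated at each visit.

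The cost is a line in the parameter list and a line or two on the comparison. No extra blood is drawn, because all nominal times to 120 minutes are shared by every PK visit.

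The downside is that AUC0-120 captures only part of a change confined to the terminal phase: in the slower-elimination case above, a 33% rise shows as 15-19%. It should therefore not be the sole comparison, and the supportive parameters need to stay.

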ANP	atrial natriuretic peptide
AP	anterior-posterior
AST	aspartate aminotransferase
AUC	area under the plasma concentration-time curve
BMC	bone mineral content
BMD	bone mineral density
BNP	B-type Natriuretic Peptide
BP	blood pressure
CFR	Code of Federal Regulations
cGMP	cyclic guanosine monophosphate
C _{max}	maximum observed plasma concentration
CBCL	Child Behavior Checklist
CNP	C-type natriuretic peptide
CNP53	C-type natriuretic peptide (53 amino acids in length)
CRA	clinical research associate
CTCAE	Common Terminology Criteria for Adverse Events
CV	cardiovascular
DCF	data clarification form
DMC	data monitoring committee
ECG	electrocardiogram
eCRF	electronic case report form
EudraCT	European Union Drug Regulating Authorities Clinical Trials
FDA	Food and Drug Administration
FGF	fibroblast growth factor
G380R	substitution in the transmembrane domain of the FGFR3 receptor at position 380
GCP	Good Clinical Practice

HIPAA	Health Insurance Portability and Accountability Act
HR	heart rate
HRQOL	health-related quality of life
IB	investigator brochure
ICF	informed consent form
ICH	International Conference on Harmonisation
ICH E6 [R2]	ICH Harmonised Tripartite Guideline: Guideline for Good Clinical Practice E6
IEC	Independent ethics committee
IgE	immunoglobulin E
IND	Investigational New Drug (application)
IP	investigational product
IRB	institutional review board
ITQOL	Infant Toddler Quality of Life questionnaire
LV	left ventricular
MAPK	mitogen-activated protein kinase
MedDRA	Medical Dictionary for Regulatory Activities
mg	milligram
mL	milliliter
msec	millisecond
NAb	neutralizing antibodies
NEP	neutral endopeptidase
NP	natriuretic peptide
NPR-B	natriuretic peptide receptor type B
PA	posterior-anterior
PD	pharmacodynamics
PI	Principal Investigator
PK	pharmacokinetics
QT	a measure of the time between the start of the Q wave and the end of the T wave
QTc-F	Fridericia's corrected QT interval
REB	research ethics board
rhCNP	recombinant C-type natriuretic peptide
SAE	serious adverse event
SAP	statistical analysis plan
SC	subcutaneous
SD	standard deviation
SOI	Statement of Investigator Form
$t_{1/2}$	elimination half-life
Tab	total antibody

Tmax	time to reach C _{max}
ULN	upper limit of normal
US	United States
WeeFIM	Functional independence measure for children
WFI	water for injection
µg/kg	microgram/kilogram

Definition of Terms:**Investigational Product (IP):**

“A pharmaceutical form of an active ingredient or placebo being tested or used as a reference in a clinical trial, including a product with a marketing authorization when used or assembled (formulated or packaged) in a way different from the approved form, or when used for an unapproved indication, or when used to gain further information about an approved use” (from International Conference on Harmonisation of Technical Requirements for Registration of Pharmaceuticals for Human Use ICH Harmonised Tripartite Guideline: Guideline for Good Clinical Practice E6 [ICH E6] (R2)).

The terms “IP” and “study drug” may be used interchangeably in the protocol.

5 ETHICS

BioMarin Pharmaceutical Inc. (hereafter referred to as BioMarin or the Sponsor) conducts its studies according to the highest ethical and scientific standards. The following sections articulate standards to which Investigators will be held accountable, as well as matters of compliance to document adherence to such standards.

5.1 Institutional Review Board or Independent Ethics Committee

Investigators are expected to interact with independent Ethics Committees (IECs) promptly, as required, during the course of the study. This includes, but is not limited to, providing appropriate documentation to support study initiation and maintaining appropriate flow of safety and other information during the course of the study and for study close-out activities. BioMarin (or designee) will assist Investigators with access to timely and accurate information and with assurance of prompt resolution of any queries.

Prior to initiating the study, the Investigator will obtain written confirmation that the institutional review board (IRB) or independent ethics committee (IEC), or Research Ethics Board (REB) is properly constituted and compliant with International Conference on Harmonisation of Technical Requirements for Registration of Pharmaceuticals for Human Use (ICH) and Good Clinical Practice (GCP) requirements, applicable laws, and local regulations. A copy of the confirmation from the IRB/IEC/REB will be provided to BioMarin Pharmaceutical Inc. (BioMarin) or its designee.

The Investigator will provide the IRB/IEC/REB with all appropriate material, including the protocol, Investigator's Brochure (IB), the Informed Consent Form (ICF) including compensation procedures, and any other written information provided to the subjects, including all ICFs translated for subjects who do not speak the local language at the clinical site. The study will not be initiated and Investigational Product (IP) supplies will not be shipped to the site until appropriate documents from the IRB/IEC/REB confirming unconditional approval of the protocol, the ICF and all subject recruitment materials are obtained in writing by the Investigator and copies are received at BioMarin or its designee. The approval document should refer to the study by protocol title and BioMarin protocol number (if possible), identify the documents reviewed, and include the date of the review and approval. BioMarin will ensure that the appropriate reports on the progress of the study are made to the IRB/IEC/REB and BioMarin by the Investigator in accordance with applicable guidance documents and governmental regulations.

5.2 Ethical Conduct of Study

It is expected that Investigators understand and comply with the protocol. This includes, but is not limited to: establishing and meeting enrollment commitments, including providing eligible subjects for study enrollment; adhering to adverse event reporting, diagnostic, or other procedures as specified in the protocol; and assuring appropriate compliance with study treatment administration and accountability.

This study will be conducted in accordance with the following:

- European Clinical Trial Directive 2001/20/EC and Good Clinical Practice Directive 2005/28/EC, for studies conducted within any European country
- US Code of Federal Regulations (CFR) sections that address clinical research studies, and/or other national and local regulations, as applicable
- ICH Harmonised Tripartite Guideline: Guideline for Good Clinical Practice E6 (ICH E6) or E6(R2) (ICH E6R2) if adopted
- The ethical principles established by the Declaration of Helsinki

Specifically, this study is based on adequately performed laboratory and animal experimentation. The study will be conducted under a protocol reviewed and approved by an IRB/IEC/REB and will be conducted by scientifically and medically qualified persons.

The benefits of the study are in proportion to the risks. The rights and welfare of the subjects will be respected and the investigators conducting the study do not find the hazards to outweigh the potential benefits. Each subject, or his/her legally authorized representative will provide written, informed consent before any study-related tests or evaluations are performed.

